4.10. Immunogenicity

Serum samples will be collected and will be tested for binding anti-AUX-I and anti-AUX-II antibodies. The subset of the samples will be tested for neutralizing antibodies if the sample results are positive for anti-AUX-I or anti-AUX-II.

5. ANALYSES POPULATIONS

The study will use the following analyses populations for data summaries and analyses.

Table 24: Analyses Populations

Population	Definition	Displays
Safety Population	The Safety Population will include all participants who receive at least 1 injection of EN3835 or placebo.	All demographic, baseline characteristics, safety and immunogenicity analyses will be summarized based on this population. Participants will be included in the safety analyses based on the actual treatment received.
Intent-to-Treat (ITT) Population	The Intent-to-Treat (ITT) Population will include all randomized participants. Treatment group assignment will be based on the randomized treatment.	The ITT population will be used for analyses of the primary and secondary endpoints.
Full Analyses Set (FAS) Population	The Full Analyses Set (FAS) Population will include all ITT participants who receive at least 1 injection of EN3835 or Placebo and have at least 1 post injection FFI pain subscale measures. Treatment group assignment will be based on the randomized treatment.	The FAS population will be used for analyses of the primary and secondary endpoints.
Modified Intent-to-Treat (mITT) Population	The modified Intent-to-Treat (mITT) Population will include all ITT participants who receive at least 1 injection of EN3835 or Placebo and have both baseline and at least one post injection FFI pain subscale measures. The treatment group assignment will be based on the randomized treatment.	This population will be used for analyses of the primary, secondary and exploratory endpoints.

6. STATISTICAL METHODS

6.1. General Methodology

All statistical tests, summary tables, data listings and graphs will be prepared using SAS Version 9.4 or higher.

Continuous data will be summarized using descriptive statistics. Discrete data will be summarized using frequency and percentages. The denominator will be based on the number of participants in the appropriate population.

For the purpose of display, the summary results will be rounded as follows:

- Minimum and maximum: Same number of decimal places as the raw data
- Mean and Median: One decimal place more than the raw data
- Standard deviation (SD): Two decimal places more than the raw data
- Percentages will be displayed with one decimal place precision. A zero count will be left blank

For categorical variables with missing values, a category documenting the frequency of missing values will be displayed in the summary tables.

Appropriate inferential statistics will be used for the primary, secondary and exploratory efficacy variables.

Tables, participant listings, graphs, and any supportive SAS output will include footnotes that will indicate:

- Date of data extraction
- Date and time of output generation
- SAS program name, including the path that generated the output

When calculating percentages, the denominator will be based on the number of participants with non-missing values. If the denominator is expected to change over time, then the denominator used to calculate the percentage will be based on the number of participants with non-missing values at each visit. Any participant removed from an analyses will be noted at the bottom of the table along with the reason the participant was removed.

Empty tables will be presented with a note stating that “No participants met criteria”.

Participant listings of all data from the eCRFs and/or vendor data as well as any derived variables will be presented.

6.2. Derived Variables

Table 25 defines the derived variables for study parameters:

Table 25: Derived Variables and Definition

Variable	Definition
Height (cm)	If height is recorded in inches, then height is equal to the recorded value multiplied by 2.54 and then rounded to 1 decimal place.
Weight (kg)	If weight is recorded in pounds, then weight is equal to the recorded value multiplied by 0.454 and then rounded to 1 decimal place.
Body Mass Index (BMI)	BMI will be computed using height measured at screening and body weight measured at respective visits as, $BMI (kg/m^2) = Weight (kg) / Height (m^2)$
Relative Day	The day of first injection of study intervention will be considered as relative Day 1.
Study Day	Study Day will be computed as, Date of Assessment – Date of Day 1 + 1 for assessment on or after Day 1, else study day will be computed as Date of Assessment – Date of Day 1.
Baseline	Baseline is defined as the last non-missing measurement/assessment prior to the first dose of study intervention. The assessments made in unscheduled visits will be considered in calculation of baseline, if the unscheduled assessment is the closest value preceding the study intervention injection.
Change from Baseline	Change from baseline will be derived as, post-baseline visit/time point value – the baseline value.
Last Date in Study	Last date in study is defined as: 
 • The date of EOS Visit (Day 57 ± 5), if the participant completes the study. • The date of early termination visits if the participant is terminated early from study at a non-scheduled visit. • The date of the latest scheduled visit if the participant is terminated early from study at a scheduled visit or lost to follow-up.
Duration (Days) of AE	AE end date - AE start date + 1
AE Onset Day	AE start date - Date of Day 1 + 1
Total Number of Nodules	Sum of all Nodules Identifier entered in Selected Nodule(s) form
Maximum of Nodule size (mm) (Caliper measurement) for participant level	Maximum of nodule size for the participant
Average Nodular Hardness (Durometer measurement) for Nodule level & Participant level	Average of nodule hardness
Area of the Nodule	$(Nodule\ Width * Nodule\ Length * \pi) / 4$ where $\pi = 22/7$
Area of Nodule for Participant level	Average of nodule area of all nodules

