 - ^d Any diagnostic, therapeutic, or surgical procedure performed within the past 10 years before the study, including those in the treatment area, should be recorded including the date, indication for, and description of the procedure.
 - ^e For women of childbearing potential.
 - ^f A complete physical examination, including height and weight at Screening.
 - ^g Testing for neutralizing antibodies will be conducted if the participant tests positive for anti-AUX-I and anti-AUX-II antibodies.
 - ^h Vital signs (ie, blood pressure, pulse, respiratory rate, and temperature) should be collected in a seated position after the participant has been sitting for 5 minutes.
 - ⁱ Vital signs should be collected in supine position prior to treatment and at 15 (\pm 5) and 30 (\pm 5) minutes post treatment.
 - ^j Opioid analgesic use is prohibited during the study. Acetaminophen and over-the-counter (OTC) nonsteroidal anti-inflammatory drugs (NSAIDs) are permitted if the investigator deems it necessary.
 - ^k Participants will complete the scale prior to evaluation by the investigator. The order of scale completion by the participant is as follows: FFI, PGIS Foot Pain Subscale, PGIC Foot Pain Subscale, PGIS Difficulty Subscale, PGIC Difficulty Subscale, PGIS Activity Limitation Subscale, PGIC Activity Limitation Subscale, PGIS PF Overall, PGIC PF Overall, Pain Intensity NRS, and Subject Satisfaction with Treatment Scale.
 - ^l Palpation for nodular consistency. For Treatment 1, only hard, firm throughout, moderately firm nodules will be treated. For Treatment 2, palpable nodules that are hard, firm throughout, moderately firm, or soft on clinical examination and measurable by caliper, that were previously treated, will be treated.
 - ^m The investigator will complete a graphic representation of the foot/feet and the location of the nodule(s) that are present.
 - ⁿ Randomized in a 1:1 ratio to either EN3835 or placebo using an Interactive Response Technology (IRT) system.
 - ^o Size of the nodule(s) will be determined by caliper and the largest width or length will be used to determine number of injections to be administered.
 - ^p On Visit Day 29, urine pregnancy testing will only be performed if the participant will receive a second treatment of study intervention.
 - ^q Including concomitant surgical and medical procedures for plantar fibromatosis and for conditions other than plantar fibromatosis.

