9.2.4. Vital Signs

At the time points listed in the Schedule of Assessments, vital signs will be obtained after the participant has been sitting for 5 minutes (minimum) and will include systolic and diastolic blood pressures, pulse rate, respiratory rate, and body temperature. The results, date, and time for all vital sign assessments will be recorded. On the day that study intervention will be administered, vital signs should be collected in supine position prior to injection and at 15 (± 5) and 30 (± 5) minutes post injection.

The investigator will review all vital sign values for clinical significance. Any vital sign value meeting the investigator's or sponsor's criteria for clinical significance will be recorded as an AE (or SAE, if appropriate).

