3.17. Vital Signs

Vital signs measurements include systolic and diastolic blood pressure, respiratory rate, pulse, and body temperature will be collected after the participant has been sitting for 5 minutes in the seated position.

Vital signs measurements will be collected at all scheduled visits as per the SoA (Table 2). On the day that study intervention will be administered, vital signs measurements will be collected in a supine position prior to injection, at 15 (± 5) and 30 (± 5) minutes post injection.

The investigator will review all vital sign values for clinical significance. Any clinically significant abnormality observed in a vital sign will be considered as an AE or SAE as appropriate.

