4.9.2.2. Potentially Clinically Important Vital Sign Values

Vital sign values are PCI, if they meet both the observed value criteria and the change from Baseline. The sponsor determined PCI criteria are presented in Table 23.

Table 23: Potentially Clinically Important Vital Sign Criteria

Parameter	PCI Low	PCI High
Systolic blood pressure	≤90 mmHg and decrease ≥20 mmHg from baseline	≥140 mmHg and increase ≥20 mmHg from baseline
Diastolic blood pressure	≤60 mmHg and decrease ≥15 mmHg from baseline	≥100 mmHg and increase ≥15 mmHg from baseline
Pulse rate	≤50 bpm and decrease ≥15 bpm from baseline	≥125 bpm and increase ≥15 bpm from baseline
Respiratory rate	≤12 brpm and decrease ≥7 brpm from baseline	≥25 brpm and increase ≥7 brpm from baseline
Temperature		≥38.3° C and increase ≥1.1 °C from baseline

PCI=potentially clinically important; bpm=beats per minute; brpm=breaths per minute.

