7.7.3. Vital Signs

Vital signs (systolic and diastolic blood pressure, pulse rate, respiratory rate, and body temperature) will be summarized by treatment group and overall (if applicable) using descriptive statistics for observed and change from Baseline values for all post-baseline assessment visits.

The PCI vital signs values will be summarized by treatment group and overall using frequency and percentages separately for each treatment. Refer to [Table 23](#) for PCI criteria.

A separate listing will be presented for vital sign results by participant.

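### Vital-sign change from baseline at Days 15, 43 and 57 subtracts a supine Day 1 baseline from seated readings, which distorts within-arm change and PCI counts

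*SAP*

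**What the plan says.** **Posture.** The general rule for the vital-signs row of the protocol's Schedule of Assessments (section 2.3, footnote h) is that readings "should be collected in a seated position after the participant has been sitting for 5 minutes". A second footnote (i) sits only on the Day 1 and Day 29 cells: "Vital signs should be collected in supine position prior to treatment", and again at 15 and 30 minutes afterwards. Protocol section 9.2.4 makes the same split, stating that on dosing days "vital signs should be collected in supine position prior to injection". SAP section 3.17 agrees: "On the day that study intervention will be administered, vital signs measurements will be collected in a supine position prior to injection". Screening and Days 15, 43 and 57 carry only the seated rule.

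**Baseline and change.** SAP section 6.2, Table 25: "Baseline is defined as the last non-missing measurement/assessment prior to the first dose of study intervention". The same table adds: "Change from baseline will be derived as, post-baseline visit/time point value – the baseline value". Neither entry has a posture condition or an exception for vital signs.

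**Use.** Change from baseline in vital signs is a stated safety endpoint (protocol section 4; SAP Table 1). SAP section 7.7.3 plans "descriptive statistics for observed and change from Baseline values for all post-baseline assessment visits", by treatment group and overall where applicable, together with PCI counts. SAP section 4.9.2.2 states: "Vital sign values are PCI, if they meet both the observed value criteria and the change from Baseline".

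**The concern.** The last vital-sign reading before the first dose is the supine one taken on Day 1 just before injection. Three of the four follow-up visits are seated. A change computed across the two postures is not a change over time alone. It also contains the difference between sitting and lying down, which has nothing to do with treatment.

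Two outputs are at stake. The tabulated mean change at Days 15, 43 and 57 could show a rise or fall in both arms when nothing had happened. The PCI counts could be too high or too low, because every PCI vital-sign criterion has a change component measured from this baseline. A reader of the study report could not separate posture from change over time, since the SAP plans no posture flag or split in these summaries.

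**Working it through.** The plan states no figure on this point, so there is none to reproduce. The check traces the posture of each reading and then works out what a mismatch does.

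**Step 1: posture of each comparison with the Table 25 baseline (supine Day 1 pre-injection)**

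| Reading | Posture | Change compares |
|---|---|---|
| Day 1, 15 and 30 min after injection | supine | supine with supine |
| Day 15 | seated | seated with supine |
| Day 29, retreated, before and after injection | supine | supine with supine |
| Day 29, not retreated | unclear | depends on posture used |
| Day 43 | seated | seated with supine |
| Day 57 | seated | seated with supine |

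Day 29 without retreatment is unclear because the schedule footnote marks the whole cell supine, while protocol 9.2.4 and SAP 3.17 tie the supine position to days on which study intervention is given.

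**Step 2: effect on the change and on the PCI limits**

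Let s be the seated-minus-supine difference in the same person, and D the change that matched postures would show.

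- Observed change at Days 15, 43 and 57 = D + s.
- A rise limit T is met when D + s ≥ T, that is, when D ≥ T − s.
- A fall limit T is met when D + s ≤ −T, that is, when the matched-posture fall is at least T + s.

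SAP Table 23 gives T = 20 mmHg systolic and 15 mmHg diastolic. With an assumed s = +5, the limits act as follows:

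- Systolic rise: 20 − 5 = 15. Systolic fall: 20 + 5 = 25.
- Diastolic rise: 15 − 5 = 10. Diastolic fall: 15 + 5 = 20.

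With s = −5 the pairs swap.

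**Step 3: effect on PCI rates (illustration on assumed values)**

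Each flag also needs an absolute value, so the altered change limit does not convert directly into a rate. A simulation of 4 million draws per setting used bivariate normal seated values, no drug effect, and a supine baseline equal to the seated value minus s. Assumed inputs:

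- Systolic: mean 128, SD 15, SD of change 12.
- Diastolic: mean 80, SD 10, SD of change 8.
- s from −8 to +8 mmHg.

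None of these is in the documents. The PCI criteria are those of SAP Table 23.

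| Assumed s (mmHg) | Mean change | Systolic high | Diastolic low |
|---|---|---|---|
| −8 | −8 | 0.6% | 1.2% |
| −5 | −5 | 1.1% | 0.8% |
| 0 (matched posture) | 0 | 2.5% | 0.36% |
| +5 | +5 | 4.8% | 0.11% |
| +8 | +8 | 6.6% | 0.04% |

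**Step 4: between-arm comparison**

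At Days 15, 43 and 57 posture is set by the visit, not by the arm. The expected difference in mean change is (D for EN3835 + s) − (D for placebo + s), which equals the difference in D. The shift cancels.

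Day 29 is the one place where it might not cancel. If participants not retreated are measured seated, the bias in the difference is s times the between-arm difference in the seated share. With assumed s = 5 mmHg and an assumed 30-point difference in that share, it is 5 × 0.30 = 1.5 mmHg. Retreatment depends on nodule status, so such a difference is possible, but the documents do not establish one.

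**The case against.** **Randomization protects the comparison.** A reader might infer that the posture shift is mixed up with the drug effect. The documents do not support that for Days 15, 43 and 57: allocation is 1:1 against placebo, summaries are by arm, and the shift is common to both. This part of the objection stands and limits the point to within-arm change and absolute PCI counts.

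**Little depends on these tables.** Vital signs are summarized descriptively, with no test. Investigators judge clinical significance and record adverse events without reference to Table 25. The stated triggers for convening the DSMB are foot injuries of Grade 3 or higher and anaphylaxis, not PCI flags. The Day 1 readings after injection are supine against supine and unaffected. All of this is fair. It makes the point modest, but it does not make a stated safety endpoint correct as derived.

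**The size is unknown.** True. The documents give neither size nor direction, and any figure rests on assumption.

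**Baseline posture may not always be supine.** The seated footnote covers the whole row, and protocol 9.2.4 can be read as asking for a seated reading at every listed visit, so a site could take both on Day 1. A missing Day 1 reading would also make the seated Screening value the baseline. This does not remove the problem: Table 25 would then let baseline posture vary between participants.

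**Day 29 change from Day 1.** A reader might infer that measuring Day 29 post-injection change from Day 1 is also an error. For retreated participants both readings are supine, and a study baseline is a conventional choice. A same-day baseline is a preference, not a correction.

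**SAP Module 2 was not available.** Posture labels in its table shells cannot be excluded, but the baseline definition belongs in Table 25.

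**Conclusion.** The point holds in limited form. Followed as written, Table 25 yields seated-minus-supine changes at Days 15, 43 and 57, and nothing in the protocol or SAP repairs this; SAP Table 28 (changes from protocol) does not mention it. The within-arm mean change is off by s, and each pair of PCI limits is moved by s in opposite senses, one easier to meet and the other harder. The expected between-arm difference in mean change at those visits is unbiased, so the tables should not be described as confounding posture with treatment.

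Confidence is high on the mismatch and low on its practical size. The PCI rates above show sensitivity to assumed values; they do not predict this trial's results. The conclusion assumes that sites follow the posture footnotes and that the Day 1 pre-injection reading is the last one before dosing. It concerns a descriptive safety endpoint and does not touch the efficacy analyses.

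**What to change.** In SAP Table 25, add a vital-sign baseline defined as the last pre-dose reading in the same posture as the post-baseline reading:

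- **Seated readings (Days 15, 43, 57):** the last seated pre-dose reading, which is Screening, or a seated Day 1 reading if one was taken.
- **Supine readings (Day 1 after injection; Day 29 before and after injection):** the supine Day 1 pre-injection reading.
- **Day 29 without retreatment:** match on the posture actually used.

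Apply the change component of the Table 23 PCI criteria to these changes, and show posture in the tables. Change from the same-day Day 29 pre-injection reading may be added as an optional extra summary.

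**Cost:** a derivation change in the SAP and its programs, using scheduled readings, with no change to study procedures. If posture is not recorded in the data, it has to be taken from the schedule, which leaves Day 29 without retreatment to be clarified with sites. The downside is that the seated baseline may be up to 28 days old, because Screening runs from Day −28 to Day −1.

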
 To assess the safety and tolerability of EN3835 in participants with plantar fibromatosis. 	
 Safety of EN3835 as assessed by incidence, severity and duration of treatment-emergent adverse events (TEAEs), adverse events of special interest (AESIs), and serious adverse events (SAEs). The change from baseline in vital signs and clinical laboratory values at each visit where these parameters are measured.

 To assess the immunogenicity of EN3835 in participants with plantar fibromatosis. 	
 Presence of anti-AUX-I and anti-AUX-II antibody titer levels in EN3835 treated-participants at Day 1 and Day 57. Presence of neutralizing antibodies to AUX-I and AUX-II in EN3835 treated-participants at Day 1 and Day 57.
Exploratory	

 To assess the overall improvement in the FFI composite score with EN3835 vs placebo. 	
 The difference between EN3835 and placebo in the mean change from Baseline (Day 1) to Day 57 on the FFI composite score, with the score of each of the 21 items ranging from 0 to 4, with 4 indicating higher severity. The mean change from Baseline (Day 1) to Days 15, 29, 43, and 57 on the FFI composite score with EN3835 vs placebo.

 To assess the overall improvement in severity of plantar fibromatosis on the Patient Global Impression of Severity (PGIS) PF Overall scale. 	
 The difference between EN3835 and placebo at Day 57 on the PGIS PF Overall score. The difference between EN3835 and placebo Days 15, 29, 43, and 57 on the PGIS PF Overall score with EN3835 vs placebo.

 To assess the overall improvement in the severity of foot pain with EN3835 vs placebo in the PGIS foot pain subscale. 	
 The difference between EN3835 and placebo at Day 57 on the foot pain subscale of the PGIS. The difference between EN3835 and placebo at Days 15, 29, 43, and 57 on the PGIS foot pain subscale, ranging from 0 ("None") to 4 ("Severe") with EN3835 vs placebo.

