9.3.1. Time Period and Frequency for Collecting AE and SAE Information

The investigator will collect all SAEs and AEs from the time of signing the informed consent form (ICF) through the EOS (Day 57) Visit. This will include any AEs that are ongoing at the time of completion/termination of the study. Participants who request to discontinue from the study will be asked to complete the 28-day post treatment Safety Follow-up Visit (or phone call if a visit is not possible) to determine the status of any ongoing AEs/SAEs or the occurrence of any new AEs/SAEs.

Investigators are not obligated to actively seek AEs and SAEs after conclusion of participant study participation. However, if the investigator learns of any SAE, including death, at any time after the participant has been discharged from the study, and the investigator considers the event to be reasonably related to the study intervention or study participation, the investigator must notify the sponsor within 24 hours as described in Section [11.3.4.2](#).

All SAEs will be recorded and reported to the sponsor or designee within 24 hours. The investigator will submit any updated SAE data to the sponsor within 24 hours of it being available. The method of recording, evaluating, and assessing causality of AEs and SAEs and the procedures for completing and submitting SAE reports are provided in Section [11.3](#).

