
 To assess the safety and tolerability of EN3835 in participants with plantar fibromatosis. To assess the immunogenicity of EN3835 in participants with plantar fibromatosis. 	
 Safety of EN3835 as assessed by incidence, severity, and duration of treatment-emergent adverse events (TEAEs), adverse events of special interest (AESIs), and serious adverse events (SAEs). The change from baseline in vital signs and clinical laboratory values at each visit where these parameters are measured. Presence of anti-AUX-I and anti-AUX-II antibody titer levels in EN3835 treated-participants at Day 1 and Day 57. Presence of neutralizing antibodies to AUX-I and AUX-II in EN3835 treated-participants at Day 1 and Day 57.

Table 1: Objectives and Endpoints (Continued)

Objective	Endpoint
Exploratory	

 To assess the overall improvement in the FFI total score with EN3835 vs placebo 	
 The difference between EN3835 and placebo in the mean change from Baseline (Day 1) to Day 57 on the FFI total score of 21 items with the score of each item ranging from 0 to 4, with 4 indicating higher severity. The mean change from Baseline (Day 1) to Days 15, 29, 43, and 57 on the FFI total score with EN3835 vs placebo.

 To assess the overall improvement in severity of plantar fibromatosis on the Patient Global Impression of Severity (PGIS) PF Overall scale. 	
 The difference between EN3835 and placebo at Day 57 on the PGIS PF Overall score. The difference between EN3835 and placebo Days 15, 29, 43, and 57 on the PGIS PF Overall score with EN3835 vs placebo.

 To assess the overall improvement in the severity of foot pain with EN3835 vs placebo in the PGIS foot pain subscale 	
 The difference between EN3835 and placebo at Day 57 on the foot pain subscale of the PGIS. The difference between EN3835 and placebo at Days 15, 29, 43, and 57 on the PGIS foot pain subscale, ranging from 0 (“None”) to 4 (“Severe”) with EN3835 vs placebo.

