6.3.3. Missing Data Handling for Safety Data

There will be no imputation of missing values for safety data, however missing relationship between AE and study intervention will be considered as related to study intervention following worst case principle.

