7.7.2. Safety by Incidence of TEAEs, AESIs, SAEs

The safety of treatment groups is assessed by incidence, severity and duration of treatment emergent adverse events (TEAEs), adverse events of special interest (AESIs), AEs resulting in study discontinuation and serious adverse events (SAEs).

The risk difference and associated 95% CI using the exact method will be presented for incidence of TEAEs, TEAEs resulting in drug discontinuation, and TEAEs leading to study discontinuation across treatments.

All AE summary tables will include only TEAEs, unless otherwise specified.

TEAEs will be summarized by SOC and PT. A participant will only be counted once per SOC and PT.

For TEAEs by severity grade (Grade 1, Grade 2, Grade 3, Grade 4 and Grade 5), if a participant has multiple events occurring in the same SOC or same PT, then the event with the highest grade will be counted.

For TEAEs by relationship to study intervention, if a participant has multiple events occurring in the same SOC or same PT, the event with the highest association (ie, related) to study intervention will be summarized.

AEs will be presented in decreasing order of the incidence at SOC level and within each SOC, in decreasing order of the incidence at the PT level.

An overall summary of TEAEs and TEAEs related to study intervention will be presented and will include:

- Total number of TEAEs reported
- Total number of TEAEs reported by severity
- Participants with any TEAE
- Participants with any serious TEAE
- Participants with any TEAE of special interest
- Participants with any Grade 3+ TEAE
- Participants with no Grade 3+ TEAEs, but at least one Grade 2 TEAE
- Participants with no Grade 3+/Grade 2 TEAEs, but at least one Grade 1 TEAE
- Participants with any TEAEs leading to drug interruption/discontinuation
- Participants with any TEAEs leading to withdrawal from study
- Participants with any TEAEs resulting in death

The following summary tables will be presented by SOC and PT:

- All TEAEs
- TEAEs by severity
- TEAEs by special interest
- Treatment related TEAEs
- Treatment related TEAEs by severity
- Serious TEAEs
- Serious treatment related TEAEs
- TEAEs resulting in death
- Study intervention related TEAEs resulting in death
- Duration of treatment related TEAEs (Duration of treatment related TEAEs (<14 days, 14 – 21 days and >21 days) (Refer to [Table 25](#) for computation of duration of AEs.)

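### An adverse event still ongoing at last contact gets no duration, so the SAP's over-21-day count is too low whenever such events occur

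*SAP*

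**What the plan says.** Duration is a named safety endpoint. Protocol section 4 assesses safety by "incidence, severity and duration of treatment-emergent adverse events (TEAEs), adverse events of special interest (AESIs), and serious adverse events (SAEs"), and SAP section 2 repeats it. The only derivation is in SAP Table 25: "AE end date - AE start date + 1". SAP 7.7.2 refers back to Table 25 for a single duration table: "Duration of treatment related TEAEs (<14 days, 14 – 21 days and >21 days").

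Three other places bear on an event without an end date:

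- SAP 6.3.3 states that "There will be no imputation of missing values for safety data", and makes an exception only for a missing causal relationship.
- SAP 6.3.4.1 mentions ongoing events, but only to settle whether they count as treatment-emergent.
- SAP 6.1 says "When calculating percentages, the denominator will be based on the number of participants with non-missing values". The same section also bases the denominator on the participants in the relevant population, and provides a row for missing values of categorical variables.

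Ongoing events are foreseen. On the collection of adverse events, Protocol 9.3.1 says: "This will include any AEs that are ongoing at the time of completion/termination of the study". Protocol 9.3.3 lets follow-up of a non-serious event stop 28 days after the last study intervention, whether or not it has resolved.

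**The concern.** An event with no end date has no duration under Table 25, and no rule in either document assigns it to a band. The SAP does not censor such events, give them an ongoing row, or count them as longer than 21 days once the dates show it. Events in the bands have resolved. Those left out had not, and they tend to be the long ones, so the error in the over-21-day count runs in one direction.

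That band carries the message of the table. The protocol's account of the earlier study (3.1, 3.2.1, 5.2 and 5.2.2) says repeatedly that most events resolved within 21 days, and 21 days is the table's top cut. If the active drug produces more persistent reactions, the under-count is larger in that arm.

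There is also a mismatch of scope. The endpoint names TEAEs, AESIs and SAEs, and 7.7.2 opens by repeating this, but the only duration table covers treatment-related TEAEs. A plantar fascial tear (an AESI) judged unrelated would have no duration summary. SAP Table 28 does not list this narrowing as a change from the protocol.

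**Working it through.** The documents give no duration figures to reproduce, so the check applies the SAP's own counting rule to ongoing events and then illustrates the possible size.

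**1. What the recorded dates already prove.** Put the last contact date in place of the missing end date. The result is a minimum duration.

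- Onset Day 1, ongoing at Day 57: 57 − 1 + 1 = 57 days. With the ±5-day visit window (Days 52 to 62) it is 52 to 62 days.
- Onset on the day of the second treatment, Day 29, ongoing at Day 57: 57 − 29 + 1 = 29 days. With both visit windows (treatment on Days 28 to 30) it runs from 52 − 30 + 1 = 23 to 62 − 28 + 1 = 35 days.
- Latest onset already known to exceed 21 days at a Day 57 visit: 57 − 36 + 1 = 22, so any ongoing event with onset by Day 36.

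All of these belong in the over-21-day band, and none is placed there.

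**2. Effect on the count, without a duration model.** Assume 100 related events, of which 20 truly last more than 21 days and half of those are ongoing at last contact. The band shows 10 instead of 20. That is 10/90 = 11.1% if ongoing events leave the denominator and 10/100 = 10% if they stay in. Both are below the true 20%.

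**3. Illustration over time.** Assume exponential durations with a true 20% over 21 days, so the share lasting beyond t days is S(t) = 0.20^(t/21). With f days of follow-up, S(f) are ongoing, and the share shown among resolved events is [0.20 − S(f)] / [1 − S(f)].

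| Onset | f (days) | S(f), still ongoing | Shown, resolved events only | Shown, all events in denominator |
|---|---|---|---|---|
| Day 1 | 56 | 0.20^(56/21) = 0.014 | 0.186/0.986 = 18.9% | 18.6% |
| Day 29 | 28 | 0.20^(28/21) = 0.117 | 0.083/0.883 = 9.4% | 8.3% |
| Equal mix | – | – | (0.186 + 0.083)/(0.986 + 0.883) = 14.4% | (0.186 + 0.083)/2 = 13.5% |

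The model counts events and uses elapsed days (56 and 28, not the inclusive 57 and 29). The SAP table counts each participant once per system organ class and preferred term, so these are not predictions of its entries.

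**The case against.** The strongest reply is that the events are not hidden. SAP 6.1 and 6.3 provide for a missing row, 6.1 calls for a note on any participant removed from an analysis, and 7.7.2 lists all adverse events, AESIs and SAEs. A reader might infer that ongoing events vanish from the report; the documents do not support that. What stands is narrower: the events are in no duration band, and a missing row does not say that they have already passed 21 days.

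A reader might also infer that SAP 6.3.3 forbids any remedy. It does not clearly do so. Section 6.3.4.1 treats ongoing as a recorded status, and placing an event already observed for more than 21 days in the top band uses observed dates, not imputed ones. The SAP is silent here.

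On size, one could take the shortest interval the visit windows allow (treatment on Day 30, final visit on Day 52, 22 days) and conclude that a true 20% would show as about 2%. That does not hold, because Protocol 9.3.3 requires ongoing events to be followed until resolution or for 28 days after the last intervention. Nor can every onset be placed at Day 29: the first treatment is planned for everyone and the second is conditional.

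Finally, duration is descriptive. No test or stopping rule uses it, the 21-day statement is background and not a hypothesis of this trial, SAEs are followed beyond 28 days where possible, and a footnote in SAP Module 2, which is not available here, might address the point. These replies limit the consequence but do not supply the missing rule.

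**Conclusion.** The point holds as a gap in a derivation rule. As written, the SAP under-counts related TEAEs lasting more than 21 days whenever an ongoing event has already passed that mark. The direction is fixed under either denominator in SAP 6.1. The size is not known from the documents and could be small: it depends on how many events are ongoing at last contact. The 9.4% to 18.9% range for a true 20% rests on exponential durations and on the assumed onset days.

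A larger bias in the active arm is a possibility, not a finding, since it depends on that arm having more persistent reactions. The efficacy analyses are unaffected. The restriction to treatment-related events is a real secondary mismatch with the stated endpoint. Both matters should be settled in the SAP before database lock, so that the handling of ongoing events is not chosen after the results are seen.

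**What to change.** - **Table 25.** For an event with no end date that is recorded as ongoing, set a censored minimum duration: last adverse event contact date − start date + 1, with a flag. Define that contact date as the later of Last Date in Study and the 28-day safety follow-up visit or call. Last Date in Study alone is not enough: for early leavers it is the early termination visit or latest scheduled visit, and they may be contacted about adverse events after that.
- **Section 7.7.2, bands.** Count a flagged event as over 21 days if its minimum exceeds 21 days. Otherwise show it in a separate row for ongoing events with 21 days or less observed. Use all participants with such an event as the denominator, and state this explicitly because 6.1 gives two rules.
- **Section 7.7.2, scope.** Produce the same table for all TEAEs, AESIs and SAEs.

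The cost is SAP wording, one flag, one derived contact date and a few extra table rows. No new assessment is needed, since the follow-up contact is already planned. The downside for the sponsor is a slightly less favourable over-21-day figure.
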